Diet Assessment. Participants will be instructed to maintain a low-polyphenol diet throughout the study. Participants will record any consumption of polyphenol-rich foods throughout the study (a record sheet will be provided, see *Polyphenol Intake Record* attachment). Participants will be instructed to abstain from polyphenol-rich foods including tea of any kind, coffee, fruits, fruit juices, chocolate, nuts, legumes, and wine (a list will be provided, see *List of Polyphenol-Rich Foods* attachment). Food records (3-d) will be evaluated at wk 0, 2, and 4 using NDSR software and the NCC Flavonoid and Proanthocyanin database to assess energy, nutrient, and flavonoid intakes as we described (19, 71).

Plasma and Urine Catechin and Catechin-metabolites. To assess the absorption, metabolism, and excretion of green tea catechins during the pharmacokinetics trial (wk 0), plasma and urine catechin and catechin-metabolites will be measured by liquid chromatography-mass spectrometry (LC-MS). Green tea catechins (EGCG, ECG, EGC, EC) and their metabolites (e.g. valerolactones) will be measured using an adapted LC-MS method (72).

Metabolic Endotoxemia. Serum endotoxin will be measured at wk 0, 2, and 4 using a commercially available fluorometric assay that assesses endotoxin-mediated activation of recombinant Factor C and subsequent cleavage of a flurogenic substrate (PyroGene rFC; Lonza) as we detailed (43).

Gastrointestinal (GI) Permeability. A 4-sugar probe procedure appropriate for human clinical study will be performed as described (73). In brief, at wk 0 and 4, participants in the fasted state will ingest a 500-mL solution of sucrose (40 g), lactulose (5 g), mannitol (1 g) and sucralose (1 g) dissolved in water. Urine will be collected over a 24-hour period to assess GI permeability. Standardized sucrose-free meals (i.e. plain bagel, cream cheese, scrambled eggs, potato chips) will

be provided during the urine collection duration. Urinary sugars will be measured by LC-MS and permeability calculated as urinary excretion (%) and excretion ratios for sugars from 0-5 hours and 6-24 hours to reflect upper and lower GI permeability, respectively (74-77).

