Upon completing the pharmacokinetics trial, the intervention phase will begin. Participants will be provided a 2-week supply of GTE-rich or placebo confections. They will be advised to consume 6 confections/ every day (2 confections/meal; 1 g GTE/d) for the following 4-wk. After 2 wk of the intervention phase, participants will complete a 3-day diet record and return for their third study visit. At this visit, fasting blood will be collected. Participants will then receive their final 2-wk supply of confections. After 4 wk, participants will complete a final 3-d diet record and perform the sugar probe test once again as described above. During each study visit, participants will have access to drinking water and use of the restroom as needed.

Sugar Probe Test. On the morning of testing at wk 0 and 4, participants will arrive at the study center after abstaining from food and only consuming water for 10-12 hours. A sugar probe test will be conducted as described (73). Upon arrival, participants will be asked to empty their urinary bladder. Subsequently, they will then be asked to ingest a drink containing 40 g sucrose, 5 g lactulose, 1 g mannitol, and 1 g sucralose dissolved in water (500 mL). Within 2-hours after ingesting the sugar test beverage, participants will be asked to consume an additional 500 mL of water. Additionally, participants will be provided with standardized sucrose-free meals during the 24-h period. All foods consumed during the 24-hour period will be free of artificial sweeteners. Urine will be collected from 0-5 and 6-24 hours in sterile containers. For each urinary collection period, participants will be provided 2-L urine collection bottles and a Styrofoam cooler with ice packs to store collected urine until they return their samples the next day.

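### Sweeteners are barred only during the 24-h sugar test, so residual dietary sucralose or mannitol may be counted as probe

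*Combined protocol and SAP*

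**What the plan says.** The test drink (III.D, Sugar Probe Test) contains 1 g each of sucralose and mannitol, 5 g lactulose and 40 g sucrose in 500 mL of water. Four statements bear on what else may be in the urine:

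- **Sweeteners.** "All foods consumed during the 24-hour period will be free of artificial sweeteners". No restriction is stated for the days before.
- **Preparation.** On the test morning "participants will arrive at the study center after abstaining from food and only consuming water for 10-12 hours". Then: "Upon arrival, participants will be asked to empty their urinary bladder". Nothing says that this urine is kept or measured.
- **Collection.** "Urine will be collected from 0-5 and 6-24 hours in sterile containers".
- **Measure** (III.C, Gastrointestinal (GI) Permeability). "Urinary sugars will be measured by LC-MS and permeability calculated as urinary excretion (%) and excretion ratios for sugars". The ratios are not named, and no baseline correction is described.

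The study-long diet instruction (III.C, Diet Assessment) tells participants to "abstain from polyphenol-rich foods including tea of any kind, coffee, fruits, fruit juices, chocolate, nuts, legumes, and wine". It names no sweetener or sugar alcohol, and neither does the Dietary Meeting paragraph in III.D. The 3-d diet records are to be evaluated for energy, nutrients and flavonoids; no check for sweeteners is mentioned.

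**The concern.** Expressing urinary sugar as a percentage of the dose assumes that all of it came from the drink. Sucralose is itself an artificial sweetener, so the protocol already treats dietary intake as interfering, yet it controls that intake only from the start of the test. Mannitol is a sugar alcohol, and a reader may not take the term artificial sweeteners to cover it even within the 24 h. The protocol keeps sugar alcohols out of the confections because of their effect on the microbiota, but does not restrict them in the participant's own diet.

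If some dietary sucralose or mannitol is still being excreted after the drink, it is added to the probe, and without a pre-dose sample the two cannot be separated later. Gut barrier function is part of the stated objective, and the plan expects obese adults to have higher permeability than healthy adults. That comparison is not protected by randomisation.

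**Working it through.** **1. No plan figure to reproduce.** The power statement (III.B) concerns serum endotoxin and gives no SD. The plan states no expected recovery or variance for permeability. The check is therefore direct arithmetic on the stated doses. Recoveries, residues and half-lives are assumptions, shown as ranges.

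**2. Coverage in time.**

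| Period | Sweetener control | Urine assayed |
|---|---|---|
| Days before the test | none stated | none |
| 10-12 h before the drink | water only | pre-dose void: no assay stated |
| 0-24 h after the drink | artificial sweeteners excluded | 0-5 h and 6-24 h |

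**3. Effect on % excretion.** Measured % = 100 × (probe recovered + residue) / dose. With a dose of 1000 mg, 1 mg of residue adds 100 × 1/1000 = 0.1 percentage point. The relative effect is (recovered + residue) / recovered.

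| Sugar | Assumed true recovery | 1-3 mg residue | 10 mg residue |
|---|---|---|---|
| Sucralose | 1% (10 mg) | ×1.10-1.30 | ×2.0 |
| Sucralose | 2% (20 mg) | ×1.05-1.15 | ×1.5 |
| Sucralose | 5% (50 mg) | ×1.02-1.06 | ×1.2 |
| Mannitol | 10% (100 mg) | ×1.01-1.03 | ×1.10 |
| Mannitol | 20% (200 mg) | ×1.005-1.015 | ×1.05 |
| Mannitol | 30% (300 mg) | ×1.003-1.01 | ×1.03 |

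**4. Effect on a ratio.** If mannitol is the denominator, as in lactulose/mannitol, the ratio is multiplied by M / (M + residue), where M is the mannitol recovered from the probe. At 10 mg of residue this is 100/110 = 0.91, 200/210 = 0.95 or 300/310 = 0.97. At 50 mg it is 100/150 = 0.67, 200/250 = 0.80 or 300/350 = 0.86. The ratio falls, so permeability would look lower.

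**5. What the fast removes.** Under a simple first-order model, the fraction left after time t is 0.5^(t / half-life).

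| Assumed half-life | After 10 h | After 12 h | After 72 h |
|---|---|---|---|
| 3 h | 10% | 6% | about 0% |
| 6 h | 32% | 25% | about 0% |
| 13 h | 59% | 53% | 2% |
| 18 h | 68% | 63% | 6% |

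The fast and void clear most of a short-lived residue but need not clear a longer-lived one. Three days of avoidance brings the residue close to zero throughout this range.

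**The case against.** The case against has real weight.

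- The 10-12 h water-only fast and the void are genuine safeguards.
- Serum endotoxin, not permeability, is the primary outcome.
- Treatment is randomised and double-blind, so residue should not differ systematically between GTE and placebo.
- Only sucralose and mannitol are affected by this argument; it does not touch lactulose or sucrose excretion.
- The test follows a cited method, and the food list is an attachment. Neither could be seen, and either may already contain a pre-test restriction.
- The diet records could reveal sweetener use without a new assay.

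All of this limits the size of the problem. It does not close the gap in the text, which states no pre-test avoidance, no baseline urine assay and no sweetener check of the records.

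A reader might infer three stronger conclusions that the documents do not support.

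1. *Contamination occurs and inflates permeability.* It is possible, not shown, and the direction depends on the measure: with mannitol as denominator the ratio falls.
2. *Inflation is 10-30%.* That range needs 1-3 mg of residue and 1% recovery, both assumed. At an assumed mannitol recovery of 10-30%, the same residue adds only 0.3-3%.
3. *Giving up tea, coffee, juice and wine shifts sweetener intake between wk 0 and wk 4.* The dietary meeting precedes the first sugar probe, and Diet Assessment applies the diet throughout the study. Other paragraphs tie it to the intervention, or to at least 3 days before the pharmacokinetics trial, so its start is unclear. A difference between the two tests is not established, and any shift would be expected in both arms.

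**Conclusion.** The concern holds as a possible source of measurement error in a non-primary outcome. As the plan is written, any sucralose or mannitol left from the diet after the fast and void would be counted as probe. The firm figure is 0.1 percentage point of excretion per mg, from the 1 g doses. Everything beyond that depends on the residue, true recovery and half-life, none of which the documents give.

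For GTE versus placebo the consequence is mainly added noise. For obese versus healthy it could be bias, but only if sweetener habits differ between the groups, and the documents say nothing on that. No sample size or power figure changes. The conclusion also assumes that neither the cited probe method nor the diet attachments already impose a washout; if one does, the protocol should state it.

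**What to change.** Add one line to the diet sheet and the Dietary Meeting instructions: avoid sucralose, mannitol and other sugar alcohols for the 3 days before each sugar probe, at wk 0 and wk 4. Use the same named list for the 24-h test period, so that mannitol is clearly covered.

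Check the 3-d diet records for these sweeteners. For this, the wk-0 record must cover the days before the first sugar probe. Test Trials implies that it does, whereas the Dietary Meeting paragraph ties it to the pharmacokinetics trial; the two should be aligned. Name the excretion ratios, so that the direction of any contamination is known.

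Optionally, keep the pre-dose void, assay it by the same LC-MS method and use it to flag contaminated tests in a sensitivity analysis. It should not be used for routine creatinine-scaled subtraction: one void assumes a constant background, and a declining one would be over-corrected, most in the 6-24 h window. Nor should flagged tests be excluded routinely, since with equal allocation there are only about 10 participants per cell (20 per health group over two arms).

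The cost is slightly more participant burden and time to read the records. Assaying the void adds about 80 LC-MS runs (40 participants × 2 tests), plus containers and storage.
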